6.1.4.3 Evaluation of New Lesions

The appearance of new lesions constitutes Progressive Disease (PD).

A growing lymph node that did not meet the criteria for reporting as a measurable or non-measurable lymph node at baseline should only be reported as a new lesion (and therefore progressive disease) if it:

- a) increases in size to ≥ 15 mm in the short axis, or
- b) there is new pathological confirmation that it is disease (regardless of size).

New effusion or ascites that appears during treatment should only be reported as a new lesion (and therefore progressive disease) if it has cytological confirmation of malignancy.

6.1.4.4 Evaluation of Best Overall Response

The best overall response is the best response recorded from the start of the treatment until disease progression/recurrence or non-protocol therapy (taking as reference for progressive disease the smallest measurements recorded since the treatment started). The

patient's best response assignment will depend on the achievement of both measurement and confirmation criteria.

For Patients with Measurable Disease (i.e., Target Disease)

Target Lesions	Non-Target Lesions	New Lesions*	Best Overall Response	Remarks
CR	CR	No	CR	
CR	Non-CR/Non-PD***	No	PR	
CR	Not evaluated	No	PR	
PR	Non-PD***/not evaluated	No	PR	
SD	Non-PD***/not evaluated	No	SD	Documented at least once ≥ 8 weeks from randomization
PD	Any	Yes or No	PD	No prior SD, PR or CR
Any	PD**	Yes or No	PD***	
Any	Any	Yes	PD	

* See RECIST 1.1 manuscript for further details on what is evidence of a new lesion.
 
** In exceptional circumstances, unequivocal progression in non-target lesions may be accepted as disease progression.
 
*** PD in non-target lesions should not normally trump target lesion status. It must be representative of overall disease status change, not a single lesion increase. Please refer to the Evaluation of Non-Target Lesions – Progressive Disease section for further explanation.
 
NOTE: Patients with a global deterioration of health status requiring discontinuation of treatment without objective evidence of disease progression at that time should be reported as “symptomatic deterioration.” Every effort should be made to document the objective progression even after discontinuation of treatment.
				

6.1.4.5 Duration of Response

Duration of Overall Response

The duration of overall response is measured from the time measurement criteria are met for CR or PR (whichever is first recorded) until the first date that recurrent or progressive disease is objectively documented (taking as reference for progressive disease the smallest measurements recorded since the treatment started).

The duration of overall CR is measured from the time measurement criteria are first met for CR until the first date that progressive disease is objectively documented.

Duration of Stable Disease

Stable disease is measured from the start of the treatment until the criteria for progression are met, taking as reference the smallest measurements recorded since the treatment started, including the baseline measurements.

To be assigned a status of stable disease, measurements must have met the stable disease criteria at least once after study entry at a minimum interval 8 weeks.

Study Parameters

7.1 Therapeutic Parameters

1. Prestudy CXR and/or scans should be done ≤ 3 weeks prior to randomization.
2. Prestudy CBC (with differential and platelet count) should be done ≤ 14 days prior to randomization.
3. All required prestudy chemistries, as outlined in Section [Q](#), should be done ≤ 14 days prior to randomization.

Assessment	Baseline	X= Each 28-day Cycle (Monthly) ¹ /alternative interval	End of treatment ⁷ (for any reason) or disease progression	Post Treatment/ Follow- up ⁶
History and physical examination	X	X		
Vital Signs (including BP)	X	X		
EKG	X	X		
LVEF	X			
Standard ophthalmological exam ¹⁰	X	Yearly or as clinically indicated		
Transthoracic echo ⁸	X	Every 3 months or as clinically indicated	As clinically indicated	As clinically indicated
Brain CT or MRI	X	Every 4 cycles if brain metastases are present on baseline scan, or more often as clinically indicated	As clinically indicated	As clinically indicated
Chest CT ²	X	Every 2 cycles or more often as clinically indicated. Confirmatory scans at least 4 weeks following initial documentation of objective response ⁹	As clinically indicated	Every 2 months until 6 months after completion of study treatment and as clinically indicated per protocol Section 5.4.3.11 for cuSCC risk management
Abdomen/pelvis CT or MRI ²	X	Every 2 cycles and as clinically indicated Confirmatory scans at least 4 weeks	As clinically indicated	As clinically indicated

Assessment	Baseline	X= Each 28-day Cycle (Monthly) ¹ /alternative interval	End of treatment ⁷ (for any reason) or disease progression	Post Treatment/ Follow- up ⁶
		following initial documentation of objective response ⁹		
CBC with differential ⁴	X	X	X	
Serum chemistry ⁵	X	X	X	
PT/PTT ⁹	X	X		
Serum or Urine Pregnancy Test ³	X			
Biological Sample Submissions		See Sections 7.2 and 0		

1. Day 1 of cycle 1 begins the first day of treatment. A cycle constitutes 28 days or 4 weeks of D+T+HCQ/ placebo therapy. Monthly tests and procedures should be done on Day 1 of each cycle, however, account for major holidays and unforeseen events such as inclement weather, scheduled visits and testing can occur +/- 1 week from the start of each cycle, as long as there is documentation as to why they did not occur according to intended schedule.
2. Standard of care imaging will be utilized for tumor measurements while on study. The preferred type of imaging is high resolution CT scans of the chest abdomen and pelvis with contrast. In cases of elevated creatinine or anaphylactic reaction to contrast dye, CT scans without contrast or MRI with gadolinium may be substituted for the abdomen and non-contrast CT for the chest. PET/CT scans may not be substituted unless the CT portion of the PET/CT is a high resolution scan with contrast.

NOTE: All visceral areas originally involved by tumor should be re-imaged every 2 cycles.

3. All females of childbearing potential must have a negative [blood test or urine test] within 14 days prior to study randomization to rule out pregnancy.
4. CBCs (with differential and platelet count) which includes WBC, ANC, Platelets, Hgb, and Hct.
5. Serum chemistries include: sodium, potassium, BUN, serum creatinine, glucose, SGOT (AST), SGPT (ALT), total bilirubin, alkaline phosphatase, LDH, albumin.
6. Follow-up: all patient will be evaluated for at least 6 months after discontinuation of study treatment and will be followed for a minimum of one year from the start of treatment, unless disease progression is reported prior to one year. One year survival information will be extracted from the medical record or by phone call for patient who have discontinued protocol treatment and completed the 6 month follow-up evaluations prior to one year from the start of treatment.
7. An End of Treatment (EOT) visits should occur 30 days (+/- 7 days) from the last dose for all patients. For patients experiencing toxicities, EOT visits should occur every 2 weeks (+/-3 days) until toxicities resolve.
8. Transthoracic echocardiogram must be completed within 28 days before starting therapy. They should be repeated every 3 months or as clinically indicated

9. As clinically indicated, with documentation of the medical necessity.
10. Any abnormalities found on standard of care eye exams will be graded and attributed to study medication by the investigator. NO additional data from routine eye exams needs to be captured.

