5.8 Duration of Follow-up

For this protocol, all patients, including those who discontinue the protocol therapy early, will be followed for response until progression, even if non-protocol-therapy is initiated. Patients will be evaluated for at least 6 months after discontinuation of study treatment and will be followed for a minimum of one year from the start of treatment, unless disease progression is reported prior to one year. One year survival information will be extracted from the medical record or by phone call for patient who have discontinued protocol treatment and completed the 6 month follow-up evaluations prior to one year from the start of treatment.

Measurement of Effect

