6.1 Antitumor Effect – Solid Tumors

For the purposes of this study, patients should be re-evaluated for response every 8 (+/-1) weeks. In addition to a baseline scan, confirmatory scans should also be obtained not less than 4 weeks following initial documentation of objective response.

Response and progression will be evaluated in this study using the international criteria proposed by the revised Response Evaluation Criteria in Solid Tumors (RECIST) guideline (version 1.1) [Eur J Ca 45:228-247, 2009]. Changes in the largest diameter (unidimensional measurement) of the tumor lesions and the shortest diameter in the case of malignant lymph nodes are used in RECIST.

The following general principles must be followed:

1. To assess objective response, it is necessary to estimate the overall tumor burden at baseline to which subsequent measurements will be compared. All baseline evaluations should be performed as closely as possible to the beginning of treatment and never more than four weeks before registration.
2. Measurable disease is defined by the presence of at least one measurable lesion.
3. All measurements should be recorded in metric notation by use of a ruler or calipers.
4. The same method of assessment and the same technique must be used to characterize each identified lesion at baseline and during follow-up.

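### The text and the study calendar give conflicting tumor-assessment schedules after treatment stops without progression, so one-year PFS can be left incompletely assessed.

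*Combined protocol and SAP*

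**What the plan says.** **Text.** Section 5.8 covers all patients, including those who stop early: each "will be followed for response until progression, even if non-protocol-therapy is initiated", and each "will be followed for a minimum of one year from the start of treatment, unless disease progression is reported prior to one year". Section 6.1 says "patients should be re-evaluated for response every 8 (+/-1) weeks", with no distinction between on and off treatment, and adds: "The same method of assessment and the same technique must be used to characterize each identified lesion at baseline and during follow-up". The note in Section 6.1.4.4 asks sites to make every effort to document progression after stopping.

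**Calendar (Section 7.1, post-treatment column).** Chest CT is scheduled "Every 2 months until 6 months after completion of study treatment and as clinically indicated per protocol Section 5.4.3.11 for cuSCC risk management". For imaging of the abdomen and pelvis the column gives no interval, only clinical indication. The NOTE under footnote 2 reads "All visceral areas originally involved by tumor should be re-imaged every 2 cycles", but footnote 1 states "A cycle constitutes 28 days or 4 weeks of D+T+HCQ/ placebo therapy". Footnote 6 repeats the one-year minimum from Section 5.8 but omits its until-progression sentence. It then says "One year survival information will be extracted from the medical record or by phone call for patient who have discontinued protocol treatment" and have finished the 6-month evaluations before one year. It names no scan for them, and neither does the matching sentence of Section 5.8.

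**Analysis.** Section 9.2 counts PFS from randomization and censors event-free patients at the last progression-free disease assessment. Section 9.4 compares Kaplan-Meier one-year PFS rates. Section 9.3 expects fewer than 4 of the 84 patients to be censored before one year.

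**The concern.** Two sites can follow this protocol in good faith and assess the same kind of patient differently. The protocol itself produces such patients. Section 4.5 requires an unblinded patient to stop protocol treatment. Table 8 allows study treatment to end after a liver event while the patient stays on for the follow-up assessments that the protocol specifies, and those are what the text and the calendar disagree on. In BAMM, 2 of 22 evaluable patients stopped before progression (Section 1.1.6).

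If the calendar is followed, an early stopper may have no complete assessment at the landmark. PFS is then censored early, or an abdominal progression is missed while a clean chest CT is taken as evidence of freedom from progression. Deaths would still be counted. If stopping differed between arms, the arm with more stopping would look better than it is. Landmark scans that were not done cannot be recovered later.

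**Working it through.** **1. The plan's own figure.** Inputs from Section 9.3: 40 evaluable per arm, one-year PFS 20% v 45%, Fisher's exact test, one-sided 0.10. Power = sum over x, y of Bin(x; 40, 0.20) × Bin(y; 40, 0.45), taken where the one-sided hypergeometric p is at most 0.10. Result: 0.8169, which reproduces the stated 81.7%. This figure is not disputed.

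**2. Does the one-year minimum reach the landmark?** It runs from treatment start, which should follow randomization by 7–10 working days, so it ends slightly after one year from randomization. It does reach the landmark, but it carries no scan. One year is 365.25/7 = 52.2 weeks, and an 8-week grid has scans at weeks 48 and 56. If the grid runs from treatment start, 10 working days is 2 weeks and the landmark falls at 52.2 − 2 = 50.2 weeks, still between the two scans. Follow-up that ends at one year can therefore end on the week-48 scan.

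**3. The calendar gap.** For a stop at month s without progression, the last scheduled chest CT is at s + 6. The chest gap before month 12 is 12 − (s + 6) when positive. The abdomen/pelvis gap is 12 − s.

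| Stop (month) | Chest gap (months) | Abdomen/pelvis gap (months) |
|---|---|---|
| 1 | 5 | 11 |
| 3 | 3 | 9 |
| 5 | 1 | 7 |
| 6 | 0 | 6 |
| 8 | 0 | 4 |

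**4. Effect on the primary test.** Simulation with 42 per arm and the Section 9.4 statistic, z = (difference in 12-month Kaplan-Meier rates) / sqrt(sum of Greenwood variances), one-sided 0.10. There were 40,000 trials per cell and 120,000 for the no-stopping baseline.

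- PFS is exponential, with monthly rate −ln(0.20)/12 = 0.134 in both arms under the null.
- Stops are uniform over months 0.5–6 and count only if they precede progression.
- After a stop, progression is missed with probability 25, 50 or 75% (assumed). Otherwise it is seen up to 6 months after the stop, with censoring there.
- An unseen progressor who dies before month 12 is an event at death. Median post-progression survival is assumed to be 13 − 5.5 = 7.5 months, from the elevated-LDH medians in Table 4.
- Stopping rates by arm are assumed, because the documents give none.

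| Stopping, HCQ v placebo | Bias in points, 25 / 50 / 75% missed | Type I error, 25 / 50 / 75% missed |
|---|---|---|
| None | 0 | 10.3% |
| 10% v 10% | about 0 | 10.5–10.8% |
| 12% v 9% | +0.1 / +0.2 / +0.2 | 10.6 / 10.8 / 11.2% |
| 12% v 4% | +0.2 / +0.5 / +0.7 | 10.9 / 11.5 / 11.9% |
| 20% v 5% | +0.4 / +0.9 / +1.4 | 11.1 / 12.1 / 13.5% |

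Monte Carlo standard error is about 0.15 points on rejection rates. With full detection through month 12, as the text implies, type I error is 10.3–10.4%.

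Sensitivity: with post-progression survival of 5 to 12 months, the ranges are 10.8–12.3% (12% v 4%) and 10.9–14.4% (20% v 5%). With stops spread over months 0.5–12 and half missed, they are 11.3% and 12.2%.

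**5. Power at 45% v 20%, same test.** With no stopping: 88.9%. With 9% stopping in both arms (2/22 = 9.1%) and 0 to 75% missed: 87.7–88.6%, with 3.1–4.1 of 84 censored before month 12. At the exact 95% limits of 2/22 (1.1% and 29.2%), half missed: 88.8% and 84.3%, with 0.5 and 12.1 censored.

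**The case against.** **The text already governs.** Section 5.8 is explicit, the 6-month and one-year figures are minimums, and footnote 6 puts the one-year minimum in the calendar too. All true. But no rule says that the text overrides the calendar, the minimum names no scan, and the only item named next is survival information. If the text governs, the calendar needs correcting.

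**The NOTE fills the gap.** Footnote 2 is attached to both imaging rows, and two cycles is 8 weeks. But a cycle is defined by days of therapy, so the NOTE sets no clear interval once therapy ends. Read across the row, it contradicts the post-treatment cells.

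**The chest CT cell may concern skin-cancer surveillance.** The reference to cuSCC sits most naturally with the clinically indicated scans. If it covers the whole cell, the calendar schedules no post-treatment chest imaging for PFS at all, which widens the conflict.

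**Materiality.** This largely stands. Every imbalance and missed-progression rate is assumed. The same test with complete data at 40 per arm has exact type I error of 10.5%, so the mildest cells are no larger than an effect of sample size. Sections 5.4.1.3 and 5.4.3.10 point to a small imbalance: overlapping toxicity is generally handled by reducing HCQ/placebo first, and patients who stop it for ocular toxicity may stay on the other drugs. Section 1.1.6 reports that responses continued in early stoppers. Exponential PFS also departs from the cure-rate pattern that Section 9.3 thinks likely. Simulated power should be compared with 88.9%, not with the 81.7% from Fisher's test on 80 patients.

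**The week-48/56 point applies on treatment too.** So it does, but a patient on treatment goes on to the week-56 scan, whereas an off-treatment patient followed only to the minimum may not.

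**Conclusion.** The concern holds. Sections 5.8 and 6.1 and the Section 7.1 calendar cannot both be followed for a patient who stops without progression, and nothing in the protocol says which prevails. The chest gap reaches the landmark for stops before month 6, and the abdomen/pelvis gap for any stop before month 12.

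The conclusion rests on contradictory instructions for the primary endpoint, not on a demonstrated bias. Bias needs both unequal stopping and missed off-treatment progressions. It is about zero with equal stopping or if the text is followed, and reaches +1.4 points (type I error 13.5%) in the most extreme imbalance of the main grid. With 9% stopping in both arms, power falls by 0.3 to 1.2 points from 88.9%. No power shortfall is shown, and the Section 9.3 censoring allowance is not shown to fail. The point is worth fixing because the correction is cheap and the missing scans could not be obtained later.

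**What to change.** Reconcile the post-treatment column, the NOTE under footnote 2 and footnote 6 with Sections 5.8 and 6.1:

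- State that patients off treatment without progression have all originally involved sites imaged at the protocol's existing 8-week interval until progression or death, or at minimum through the first assessment at or after 12 months from randomization.
- State that the one-year survival contact does not replace the PFS assessment.
- Report by arm how many patients stopped without progression and had no assessment at or after 12 months.

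The cost is rewording in the calendar, the NOTE, footnote 6 and Section 5.8, plus a few standard-of-care scans in about 5–6 of 84 patients if 9% stop early (5.6 in the simulation). Section 5.8 already implies those scans. Sample size and the stated power do not change.

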7.2 Biological Sample Submissions

1. Specimens are to be submitted as outlined in Section [Q](#).
2. All specimens submitted must be entered and tracked via the online ECOG-ACRIN Sample Tracking System (STS).

Rev Add2

Biological Materials	Prior to Start of Treatment	Cycle 1, Day 7 (+/- 2 days)	Cycle 2, prior to start of treatment (+/- 1 week)	Cycle 3, prior to start of treatment (+/- 1 week)	Progression
Submit from patients who answer 'Yes' to 'I agree that my tissue and blood samples and related health information may be kept in a Biobank for use in future health research.' ⁵					
Archival Tumor Tissue Biopsy ¹	X				
Plasma (one 10mL EDTA purple top tube) ²	X	X ⁶	X ^{6,7}	X ⁷	
Submit from patients who answer 'Yes' to 'I agree biopsies may be done to obtain research samples.'					
Serial Tumor Tissue Biopsy ^{1,4}	X		X ³		X

1. Tumor tissue and related pathology reports are to be submitted within one month of randomization or collection.
2. Kits are being provided for the collection and shipment of the plasma specimens. See [Appendix VI](#) for instructions. Kit orders will on average be delivered within three (3) business days from when the order was placed.
3. Either week 1 +/- 2 days or week 4 +/- 1 week or both. The investigator will use clinical judgement to choose time points for the second on-treatment biopsy and whether both may be collected.
4. Serial biopsies are to be obtained from patients that have easily accessible lesions.
5. As outlined in the Informed Consent patient participation in tumor tissue and plasma submissions is optional. Institutions must offer participation in these optional studies to all patients.
6. For patients submitting tumor tissue from serial research biopsies plasma collection will be prior to start of treatment, Cycle 1 Day 7 (+/- 2 days, and prior to start of Cycle 2 treatment (+/- 1 week).
7. For patients not submitting tumor tissue from serial research biopsies plasma collection will be prior to start of treatment, prior to start of Cycle 2 treatment (+/- 1 week), and prior to Cycle 3 treatment (+/- 1 week).

Drug Formulation and Procurement

8.1 Dabrafenib mesylate (NSC 763760)

8.1.1 Chemical Name

N-[3-[5-(2-Amino-4-pyrimidinyl)-2-(1,1-dimethylethyl)-1,3-thiazol-4-yl]-2-fluorophenyl]-2,6-difluorobenzene sulfonamide, methanesulfonate salt

8.1.2 Other Names

GSK2118436B, GSK2118436A (free base), Tafinlar®

8.1.3 Classification

BRAF inhibitor

8.1.4 CAS Registry Number

1195768-06-9

8.1.5 Molecular Formula

C₂₃H₂₀F₃N₅O₂S₂ · CH₄O₃S

8.1.6 M.W.

615.68 (mesylate salt)

8.1.7 Mode of Action:

Dabrafenib mesylate is a potent and selective BRAF kinase inhibitor. This inhibition suppresses downstream activity of pERK, a biomarker, and has antiproliferative activity against BRAF mutant tumors. The mode of action is consistent with ATP-competitive inhibition.

8.1.8 How Supplied

Commercially available as capsules.

50 mg capsules: Dark red capsule imprinted with 'GSTEW' and '50mg' available in bottles of 120 (NDC 0078-0682-66). Each bottle contains a silica gel desiccant.

75 mg capsules: Dark pink capsule imprinted with 'GSLHF' and '75mg' available in bottles of 120 (NDC 0078-0681-66). Each bottle contains a silica gel desiccant.

8.1.9 Storage

Store at 25°C (77°F); excursions permitted to 15°C to 30°C (59°F to 86°F)

8.1.10 Stability

Refer to the package label for expiration.

8.1.11 Route and Method of Administration

Oral administration. Take dabrafenib mesylate can be taken on an empty stomach either 1 hour before or 2 hours after a meal. If a dose is missed, it should not be taken later.

8.1.12 Potential Drug Interactions

In vivo data shows that metabolism of dabrafenib mesylate and its metabolites is mediated by CYP3A4 and CYP2C8 with minor contributions by CYP 2C9 and 2C19. Use caution if strong inducers or inhibitors of CYP2C8 or 3A4 are co-administered with dabrafenib. Although *in vitro* studies indicate dabrafenib mesylate and its metabolites are substrates for P-glycoprotein (P-gp) and BCRP transporters, the apparent high oral bioavailability and permeability indicate modulation of efflux transporters will have minimal impact on dabrafenib pharmacokinetics.

Dabrafenib mesylate and its metabolites showed moderate inhibition of CYP 2C8, 2C9, 2C19 and 3A4 in human liver microsomes. Use caution in patients who are taking sensitive substrates of these enzymes. Additionally, dabrafenib and its metabolites showed inhibition of OATP1B1, OATP1B3, OAT1, OAT3 and OCT2 transporter systems; however, the drug-drug interaction risk is believed to be low based on clinical exposures.

Neither dabrafenib nor its metabolites show inhibition of P-gp *in vitro*, but are moderate inhibitors of BCRP. Dabrafenib may affect the pharmacokinetics of co-medications with narrow therapeutic index whose absorption or clearance depends on BCRP-mediated transport.

In vitro, dabrafenib mesylate induces CYP 2B6 and 3A4 and possibly CYP 2C8, 2C9 2C19, UDP glucuronosyltransferase and P-gp.; although *in vivo*, the overall effect of dabrafenib induction is as a mild inducer of CYP2C9 and moderate inducer of CYP3A4. Use caution in patients who are taking substrates of these pathways, such as warfarin or hormonal contraceptives and monitor for loss of efficacy.

Dabrafenib solubility is pH-dependent but is not expected to be reduced when co-administered with pH elevating agents like proton pump inhibitors.

